We intend to meet this unfulfilled need by developing **Shine**, a mobile intervention designed specifically for African American TGW that is theory-based, individually-tailored, and empowering. Based on the IMB-model, users receive three types of personalized text messages: informational, motivational, and skill-building. Based on the Model of Gender Affirmation, additional messaging provides strategies for gaining intra- and interpersonal forms of gender affirmation. These text messages are supplemented by two types of web-based videos: unscripted peer narratives and educational instruction. Links to these videos are integrated into the messaging to enhance the trans-specific understanding of gender affirmation within our IMB framework.

We plan to test the effectiveness of **Shine** in a randomized controlled trial with 215 African American TGW. Participants will be randomly assigned to receive either the mobile **Shine** intervention or a YouTube playlist of CDC-developed videos about HIV for transgender adults. Before and at 6-months post-randomization, we will assess participants' risk for HIV transmission, practice of individual recommended behaviors based on HIV status (i.e., condomless anal sex, ART adherence, PrEP interest/uptake), barriers to those behaviors, gender affirmation, and social support.

3. Indicate the total number of subjects and the number of sites:

Number of subjects: 215

Number of sites: 1 (1 recruitment partner [Trans Women of Color Collective], with recruitment occurring in person and online throughout the United States)

4. Indicate the characteristics of study population:

(a) Gender: Males yes no X

Trans Females yes no _____

(b) Age range: from 18 to no upper limit

(c) Racial and Ethnic Groups:

| | | |
|------------------------|---|--|
| Caucasian | yes _____ | no  _____ |
| Black | yes  _____ | no _____ |
| Hispanic | yes  _____ | no _____ |
| American Indian | yes _____ | no  _____ |
| Alaskan Native | yes _____ | no  _____ |
| Asian/Pacific Islander | yes _____ | no  _____ |
| Other (specify) _____ | | |

(d) Justify any exclusion of specific gender, age, and racial or ethnic groups:

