15. Indicate how you will determine whether the subjects (or their surrogates) understand the information that was provided in the consent document:

All participants will be given the opportunity to ask questions after the study coordinator has explained the study and before they receive the informed consent text message. In addition, after reviewing the informed consent, participants will be asked again if they have any questions or want more information on any aspect of the study. Finally, all participants will be provided with the names and phone numbers of the study PI and the ISA IRB. They will be instructed to call the PI or ISA if they have questions related to requirements of participation or for questions related to the nature of the study.

16. Summarize in a narrative what actually will be done to the subjects during their participation in the study.

(A) a clear description of what is being done for research purposes and what is being done as part of standard clinical care;

All described procedures, including the completion of research surveys, the **Shine** program, and the control videos, are part of the research process. The study procedures will take place over a 6-month period. First, all consented participants will complete the baseline research survey via telephone (see Appendix D: Research Surveys), be randomized to the experimental or control condition, and review their assigned materials (either the **Shine** program or a YouTube playlist of CDC-developed videos on HIV prevention and treatment among transgender adults). While the **Shine** intervention is designed to be completed in 1-2 months, participants will have up to 3 months to complete the intervention. Three months after sending the “join” text, experimental participants’ access to **Shine** will be terminated. Six months after the first research appointment, all participants will again be contacted by phone to complete the follow-up survey. After completing the follow-up survey, participants in the control condition will have access to the **Shine** program. Please see Appendix E: Study Protocol for more information on these procedures. In addition, please see Appendix F: Reminder Protocol and Appendix G: Retention Protocol for details on additional contact with participants.

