(B) a list of tests and procedures that will be performed for research purposes (e.g. blood tests, urine tests, cultures, interviews, questionnaires, surgical procedures, cardiac catheterization, pulmonary function tests, X-rays, scans, etc.);

Please see Appendix D: Research Surveys for all research items.

(C) a brief description of the analyses that will be performed on the biologic or non-biologic (i.e. questionnaires) samples collected

The data will derive from a randomized controlled trial (RCT) with random assignment of individual participants to one of two study conditions (intervention vs. control). Data will be collected at baseline and at 6 months post-baseline. The primary outcome measure is a binary composite HIV transmission risk score. This dichotomous metric is calculated by measuring whether a participant or her partner consistently used at least one effective method for reducing HIV transmission risk (i.e., adherence to biomedical [ART or PrEP] and behavioral [condoms, serosorting] strategies) during each instance of anal sex over the past month. Every anal sex act must be protected by one of these methods to receive an overall composite score of 0. The individual behavioral components of the composite score (i.e., percentage of condomless anal sex, serosorting, PrEP or ART adherence) will serve as secondary measures. In addition, specific outcomes by HIV status will include HIV medical care utilization and adherence, HIV testing, and PrEP knowledge, interest, and uptake. Finally, further secondary measures will assess gender affirmation, well-being, social support, and sexual communication. All measures are self-report and assessed using established scales that have evidence of reliability and validity.

Binomial logistic regression will be the main analytic technique for the primary outcome (composite HIV transmission risk score) and other non-continuous measures. For continuous measures, hierarchical linear modeling (HLM) will be used. All models will control for any demographic covariate (e.g., age) that varies at the .2 significance level due to randomization failure at baseline.

(D) a list of investigational devices that will be used, indicate if they are classified as significant risk (SR) or non-significant risk (NSR) devices and whether there is an IDE or there is an application to the FDA for an IDE if the device is SR;

N/A

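### The two-wave HLM for continuous secondary outcomes is unspecified; in its usual form it is a change-score analysis, less precise than adjusting for the baseline score

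*Combined protocol and SAP*

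**What the plan says.** The analysis plan is a short part of item 16(C).

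- Continuous outcomes: "For continuous measures, hierarchical linear modeling (HLM) will be used". No fixed effects, random effects, covariance structure or treatment contrast are given.
- Timing: "Data will be collected at baseline and at 6 months post-baseline". Item 16(A) puts the first wave before allocation: "all consented participants will complete the baseline research survey via telephone (see Appendix D: Research Surveys), be randomized to the experimental or control condition".
- Covariates: "All models will control for any demographic covariate (e.g., age) that varies at the .2 significance level due to randomization failure at baseline". The baseline value of the outcome is neither named nor excluded.
- Outcomes concerned: the continuous measures among the secondary outcomes. Besides the behavioural components of the composite, "further secondary measures will assess gender affirmation, well-being, social support, and sexual communication".
- Not concerned: "The primary outcome measure is a binary composite HIV transmission risk score", which is analysed by logistic regression.
- Size: "Number of subjects: 215" (item 3). No effect size, power, correlation or dropout rate is stated.

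**The concern.** Women are randomised individually and no clustering is described, so the only hierarchy is two waves within a woman. The natural HLM for such data takes both waves as outcome rows and reads the treatment effect from the arm-by-time term. With two waves, a random slope cannot be separated from residual error, which leaves a random intercept. If each arm also has its own free baseline mean, the model estimates the chance baseline gap between arms and subtracts it in full. Because the baseline survey precedes randomisation, that gap is zero in expectation. Subtracting all of it, instead of the part that predicts follow-up, generally adds noise.

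At stake is the precision of outcomes such as gender affirmation and social support, in a population that item 13 describes as hard to reach. An unstated model also leaves the choice of treatment-effect coefficient open until the data are in hand.

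**Working it through.** **Inputs.** From the documents: N = 215, two arms, two waves, baseline before randomisation. Assumed, because the documents give none: 1:1 allocation (108 and 107), two-sided 5% test, effect 0.3 SD, no dropout unless stated, and a baseline-to-follow-up correlation rho of 0.3 to 0.7 (wider range 0.2 to 0.8). The plan has no power figure to reproduce.

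**Step 1: what the usual model estimates.** With complete data, the random-intercept model with arm, time and arm-by-time fits the four cell means exactly. Its arm-by-time coefficient is therefore

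(6-month mean − baseline mean, intervention) − (6-month mean − baseline mean, control),

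the difference in mean change. In simulated two-wave data (N = 215; 25 data sets at each of rho 0.3, 0.5 and 0.7) the two estimates agreed to about 3e-15 with the same SE. With 20% random dropout at rho 0.5 the identity is approximate: estimates differed by up to 0.08 SD. Mean SEs were then 0.146 for the HLM, 0.150 for completers' change scores and 0.130 for the baseline-adjusted analysis.

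**Step 2: variance, equal SDs (SD = 1 at both waves).** Per woman:

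- change score: 2(1 − rho)
- baseline-adjusted: 1 − rho²
- ratio: 2(1 − rho) / [(1 − rho)(1 + rho)] = 2/(1 + rho)

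SE = √[variance × (1/108 + 1/107)] = √[variance × 0.0186].

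| rho | variance, change / adjusted | ratio | SE, change / adjusted | power at 0.3 SD, change / adjusted |
|---|---|---|---|---|
| 0.3 | 1.40 / 0.91 | 1.54 | 0.161 / 0.130 | 46% / 63% |
| 0.5 | 1.00 / 0.75 | 1.33 | 0.136 / 0.118 | 59% / 72% |
| 0.7 | 0.60 / 0.51 | 1.18 | 0.106 / 0.097 | 81% / 87% |

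Over rho 0.2 to 0.8 the excess variance runs from 67% to 11%. At rho 0.5 the adjusted analysis would need about 215 × 1.5/2 = 161 women for the precision the change score gets from 215. Below rho 0.5, 2(1 − rho) exceeds 1, so the change score is less precise than ignoring baseline altogether (rho 0.3: SE 0.161 against 0.136).

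**Step 3: unequal SDs.** Let the follow-up SD be 1 and the baseline SD be k. The change-score variance is 1 + k² − 2·rho·k and the adjusted variance is still 1 − rho². The excess is (k − rho)², which is never negative but is zero when k = rho. At k = 0.7 (assumed):

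- rho 0.3: 1.07/0.91 = 1.18, so 18% larger
- rho 0.5: 0.79/0.75 = 1.05, so 5% larger
- rho 0.7: 0.51/0.51 = 1.00, no loss

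**Step 4: does the form of the remedy matter?** One option is to keep the random intercept and drop the arm main effect, so that both arms share a baseline mean. With equal SDs this works (mean SE 0.117 at rho 0.5, against 0.118 for ANCOVA). But a random intercept forces equal variances at both waves. With baseline SD k = 0.6 (assumed), the model uses b = 2·rho·k/(1 + k²) as its baseline weight. It reports variance [(1 + k²)/2](1 − b²), while the true variance is 1 − 2b·rho·k + b²k².

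- rho 0.3: b = 0.36/1.36 = 0.265; reported 0.632 (SE 0.108), true 0.930 (SE 0.132)
- rho 0.5: b = 0.60/1.36 = 0.441; reported 0.548 (SE 0.101), true 0.805 (SE 0.122)

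In both cases the nominal 5% test is really at 2Φ(−1.96 × √(reported/true)), about 11%. Simulations in these settings gave 8% to 15%. ANCOVA's true SEs here are 0.130 and 0.118 (variances 0.91 and 0.75); the change score's are 0.136 and 0.119 (variances 1.00 and 0.76).

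**The case against.** The strongest objection is that the criticised model is not in the documents. Item 16(C) names HLM and nothing more, and an HLM with a common baseline mean, or with baseline as a covariate, need lose nothing. A reader might infer that the trial will run change-score analyses and that every continuous outcome will have an unnecessarily wide interval. The text does not say so. A reader might also take the covariate rule to shut out the baseline outcome score. It does not: it says which demographics must enter, contains no word limiting the models to these, and sits in a form item that asks for a brief description. This objection stands in full, and the point is conditional for that reason.

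Second, the 2/(1 + rho) ratio needs equal SDs and complete data. The inclusion criteria (item 5) require recent condomless anal sex with a serodiscordant or risky partner and inconsistent ART or PrEP use. The baseline spread of those behaviours may therefore be narrower than at 6 months, and Step 3 shows that the loss can then almost vanish. Nor is 215 the denominator for ART or PrEP measures, which depend on HIV status. This also stands. Equal SDs remain plausible for the psychosocial scales, on which nobody is selected.

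Third, this is an efficiency matter for secondary outcomes. True. But the plan gives no sign that an efficient model is intended, and the adjusted analysis uses data already collected.

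**Conclusion.** The point holds in conditional form. The HLM is unspecified, and its usual two-wave form amounts to a change-score analysis. Where SDs are similar at both waves, that form carries 54%, 33% or 18% more variance than a baseline-adjusted analysis at rho 0.3, 0.5 or 0.7. Power for a 0.3 SD effect is then lower by 17, 13 or 6 percentage points (63 − 46, 72 − 59, 87 − 81). These figures rest on assumed values of rho, equal SDs, 1:1 allocation and complete follow-up, none of which the documents supply. With a smaller baseline SD the loss is lower and may be near zero.

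The effect is on precision only: the change-score estimate is unbiased under randomisation, and the primary analysis is unaffected. It is worth correcting because a better method is available at almost no cost, and because naming the model also fixes the treatment-effect coefficient in advance.

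**What to change.** In item 16(C), state for every continuous outcome a linear regression of the 6-month score on arm and the baseline score of that same outcome. Name the arm coefficient at 6 months as the treatment effect. Say that the baseline score enters whatever the .2-level imbalance tests show.

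If a two-wave model is preferred, specify a common baseline mean for both arms and an unstructured covariance. Do not pair the common baseline mean with a random intercept alone, since its equal-variance constraint can inflate type I error (Step 4).

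Cost: one sentence and one degree of freedom per model. No new data are needed, because the baseline survey is already completed before randomisation.

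### The only covariate rule is a p < .2 imbalance test on demographics; baseline risk behaviour and HIV status are not named for adjustment

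*Combined protocol and SAP*

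**What the plan says.** Item 16(C) assigns binomial logistic regression to the primary outcome and other non-continuous measures, and hierarchical linear modelling (HLM) to continuous ones. It then gives a single covariate rule: "All models will control for any demographic covariate (e.g., age) that varies at the .2 significance level due to randomization failure at baseline".

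The primary outcome is a binary composite over the past month: "Every anal sex act must be protected by one of these methods to receive an overall composite score of 0". Its components are secondary measures: "percentage of condomless anal sex, serosorting, PrEP or ART adherence". HIV status enters the analysis text only to define outcomes: "specific outcomes by HIV status will include HIV medical care utilization and adherence, HIV testing, and PrEP knowledge, interest, and uptake". Nowhere in the document is HIV status, or any baseline risk behaviour, named as a covariate or stratification factor.

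These data come before allocation. Item 16(A) has it that "all consented participants will complete the baseline research survey via telephone (see Appendix D: Research Surveys), be randomized to the experimental or control condition", and item 2 lists HIV transmission risk and the individual behaviours among what is assessed at that point.

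Two appendices could add to this. Item 16(B) says "Please see Appendix D: Research Surveys for all research items", and item 16(A) says "Please see Appendix E: Study Protocol for more information on these procedures". Neither is in the file.

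**The concern.** Participants are randomised individually, so any baseline difference is chance unless allocation was subverted. A test at the .2 level then flags one variable in five by design, and calling this a failure of randomisation misreads it.

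The rule also selects on the wrong property. A covariate earns its place by predicting the outcome, not by differing between arms. A demographic that does predict the outcome is left out in about four trials in five. Because the rule covers demographics only, it would not, as written, adjust for a chance imbalance in HIV status or baseline risk.

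At stake is power in the primary analysis: predictors already collected may go unused.

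**Working it through.** **No plan figure to reproduce.** The document gives N = 215 (item 3) without alpha, power, effect size, event rate, allocation ratio or dropout. Everything below except N and the .2 threshold is assumed.

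**1. How often the rule fires in a sound trial.** For k independent demographics, P(at least one p < .2) = 1 − 0.8^k.
- k = 5: 1 − 0.328 = 67%
- k = 6: 1 − 0.262 = 74%
- k = 8: 1 − 0.168 = 83%

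With pairwise correlation .3 (500,000 draws) these become 63%, 70% and 78%.

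**2. Chance imbalance that the rule ignores.** With 1:1 allocation, the SD of the between-arm difference in HIV prevalence π is √(4π(1 − π)/215). At π = 0.4 this is √(0.96/215) = 0.067, so P(difference of 10 points or more) = 2Φ(−0.10/0.067) = 13.5%. At π = 0.2 and 0.5 it is 6.7% and 14.3%.

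**3. Power at N = 215.** Simulation with 8,000 runs per scenario:
- 1:1 allocation, control risk 60%, treatment log-odds −0.85 (conditional odds ratio 0.43), HIV prevalence 40%, six independent demographics.
- The list is the baseline proportion of acts without a condom, an indicator for no anal sex, and HIV status.
- The underlying score of that proportion correlates .80 (good measure) or .42 (poor measure) with latent risk.
- 10% report no anal sex. Of the rest, 10% skip the item and are filled with the both-arm mean.

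Scenario columns give log-odds for latent risk / HIV status / each demographic. Power in %:

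| Scenario | Unadjusted | .2 rule | List, good | List, poor | List + six, good | List + six, poor |
|---|---|---|---|---|---|---|
| A: 0 / 0 / 0 | 88.4 | 87.1 | 87.2 | 87.2 | 86.9 | 86.7 |
| B: 0.4 / 0.3 / 0.1 | 85.0 | 83.7 | 84.5 | 83.9 | 84.3 | 83.8 |
| C: 0.8 / 0.6 / 0.1 | 77.6 | 75.6 | 79.0 | 77.1 | 79.0 | 77.2 |
| D: 1.4 / 0.6 / 0.1 | 61.9 | 60.0 | 66.8 | 62.9 | 66.9 | 63.2 |
| E: 0.8 / 0.6 / 0.3 | 71.0 | 70.2 | 72.1 | 70.5 | 75.6 | 74.1 |
| F: 0.8 / 0.6 / 0.5 | 61.2 | 61.8 | 61.4 | 60.2 | 70.8 | 69.3 |

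Differences in points, taken before rounding (so they may differ from the table by 0.1):
- List minus rule, A to D: 0.1, 0.8, 3.3, 6.9 (good); 0.1, 0.3, 1.5, 2.9 (poor). Paired SE is 0.2 to 0.4.
- List minus unadjusted, A to D: −1.2, −0.6, +1.4, +4.9 (good); −1.3, −1.1, −0.5, +0.9 (poor).
- List minus rule, E and F: +1.9 and −0.4 (good); +0.3 and −1.6 (poor). With the six demographics added to the list: +5.4 and +9.0 (good); +3.9 and +7.5 (poor).

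**4. Stability.** Two smaller repeats on the same inputs (3,000 and 2,500 runs, about 1 point of error per power figure) gave list minus rule, A to D, of 0.3, 0.4, 2.7, 6.1 and 0.4, 0.8, 3.1, 5.0 (good), and 0.1, 0.2, 1.2, 1.9 and 0.3, −0.2, 1.6, 1.9 (poor). With 172 analysed (20% loss, assumed), the 8,000-run gains were 0.0, 0.7, 3.3, 6.2 (good) and 0.0, 0.3, 1.4, 2.4 (poor).

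**5. What the selection step itself costs.** Compared with fixing the same six demographics, the rule loses about 0 to 0.4 points in A to D, but 2.6 and 6.3 points in E and F. In A to D the two log odds ratios differ by an SD of about 0.04, against a sampling SD of 0.28.

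**6. Type I error** (good measure; A, C, D): 5.1%, 4.9%, 4.9% for the rule and 5.0%, 5.3%, 5.2% for the list.

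**The case against.** Item 16(C) asks only for a brief description, in an ethics-board form. The sentence does not say that nothing else enters the models, and an appendix may name more. That stands: it is certain that the .2 rule is stated, but not that baseline predictors will go unused.

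Validity is not threatened. A demographic is left out when it is roughly balanced, so the loss is precision, not bias. That also stands.

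The power gain rests wholly on assumed inputs and is small in the poor-measure case, where the list is below no adjustment in three of scenarios A to D. That case may be the nearer one, because the composite also counts ART, PrEP and serosorting. Holding the marginal effect fixed instead (60% against 41%, assumed; 2,500 runs), the gains over the rule are about 1.1, 1.5, 2.4 and 5.7 points (good) or 0.6, 0.6, 1.1 and 1.4 (poor). The modest size stands. But the plan's stated method is the rule, not no adjustment, and in A to D the list matches or beats that rule within simulation error.

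HLM fitted to baseline and 6-month data probably already carries the baseline value of continuous outcomes. This is likely but unstated, and does not reach the logistic primary model.

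**Conclusion.** The concern holds. The stated rule treats ordinary chance differences as a fault in randomisation, chooses covariates without regard to prognosis, and omits the variables most likely to predict the outcome. The consequence is lost power, from essentially none to about 7 points against a fixed list, and at most about 3 points if baseline behaviour is a poor proxy for risk. These sizes depend on assumed event rates, effect size, HIV prevalence, prognostic strengths and number of demographics. The flag rates depend only on the number of candidates and their correlation. This is a cheap improvement that should be made, not a threat to the trial's validity.

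**What to change.** Delete the sentence, including its reference to failed randomisation, and put in its place:

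> All models adjust for a fixed list, set before any outcome is examined by arm and used whatever the baseline balance: (1) a baseline measure of the outcome behaviour. For the primary outcome this is the proportion of anal sex acts without a condom, set to 0 with an indicator if none were reported; for other outcomes it is the baseline value of that outcome, unless the HLM already includes it. (2) HIV status, omitted for outcomes defined within one HIV-status group. (3) Optionally, any demographic, such as age, named here because it is expected to predict the outcome. Skipped baseline items are set to the mean over both arms. No covariate is added or dropped because of a baseline test.

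Adjustment for any unlisted imbalanced demographic belongs in a labelled sensitivity analysis. A graded measure is preferred because entry (item 5) requires condomless sex plus inconsistent ART or PrEP use in the past 3 months, which may leave the binary composite little baseline variation. The handling of skipped items is needed because item 16(F) lets participants skip questions.

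The same edit should settle three details: whether baseline ART or PrEP adherence joins the list, how unknown HIV status is coded, and that the adjusted odds ratio is conditional on the covariates.

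Cost: wording only, since the behavioural measures are already collected. On the assumed inputs, if the covariates prove weak the list is about 1 point below no adjustment (up to 2.0 with 172 analysed). If strong demographic predictors are left off, it can be up to 1.6 points below the present rule; item (3) is there to prevent that. An unlisted imbalanced demographic would no longer enter the primary model.
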